current regulatory guidance ([FDA 2019](#), [EMA 2017](#)), the assay design will employ a screening tier (no inhibition), confirmatory tier (competitive inhibition with excess drug), characterization tier (competitive inhibition with excess human insulin and excess NovoLog®) and titration tier.

All samples will be subjected to an initial screening assay (Tier 1), and those with %B/T values greater than or equal to a run-specific screening cut point will be scored as putative ADA positives.

Screen positive samples would then undergo the confirmatory assay (Tier 2), and samples exhibiting percentage inhibition greater than the confirmatory cut point will be scored as confirmed positive. The cut-point for the screening assay will be based on the %B/T response using normal human serum from treatment naïve individuals and use a 5% false positive error rate. The confirmatory cut points will be determined for both ADA and insulin cross-reactive ADA based on the % inhibition of tracer binding using excess MYL-1601D and human insulin, respectively. Each confirmatory cut-point will be determined using normal human serum from treatment naïve individuals and employ a 1% false positive error rate. The percent inhibition determined using NovoLog as inhibitor would be reported for comparison purposes.

All confirmed positive samples will be evaluated for titer (Tier 3) by serially diluting the samples (2-fold dilution steps) and estimating the titer as the interpolated dilution at the run specific titer cut point (determined from the screening data using normal human serum from treatment naïve individuals at 0.1% false positive error rate). In addition, all samples identified as ADA positive will be further evaluated for neutralizing antibodies using a separate cell-based assay.

The labeled drug product (^{125}I -MYL-1601D) is used as the capture reagent in the RIPA, which allows antibodies that arise from any insulin aspart epitope to be bound and detected. The specificity of capture reagent binding is confirmed by treatment with excess unlabeled MYL-1601D, which will interrupt binding for any of the insulin aspart epitopes. Because this assessment theoretically detects all antibodies that may arise due to drug exposure, it will be used to determine patient sample ADA status.

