For continuous-valued ADA titer, missing values prior to the last observed visit will be filled in with MCMC imputation to make the dataset monotone. Missing values after discontinuation will be imputed by regression imputation of the monotone missing dataset. If there are at least 6 retrieved dropouts in each treatment arm, then a pattern mixture model estimated from the retrieved values will be used for regression imputation of missing values. Otherwise, the complete case missing values method will be used. Missing values for the binary response variable will be imputed using a logistic regression multiple imputation model. A monotone missingness pattern will be created by taking a random draw from the binomial distribution with the same probability as the observed responses from the same treatment group at the same visit.

Pattern mixture models will be fit separately for ADA binary response and for ADA titer. Binary response will be imputed using a logistic regression imputation model, while ADA titer will use a continuous-valued regression. Independent variables in the regression will include the values at all prior visits. Each imputation will be repeated 30 times with a seed of 40872021 for ADA binary response and a seed of 41671703 for ADA titer. Code for the multiple imputation analyses is presented in Appendix 10.1.

If baseline value is missing, the missing baseline value will be imputed with six imputations based on binomial distribution using probability of no missing baseline values from same treatment group.

After imputation, the dataset containing the imputed visitwise TEAR positive or negative status binary response and the dataset containing the imputed ADA titer values will be merged by subject, visit, and imputation number. The Week 24 values will then be used to assign the status of TEAR positive or negative, as follows:

If the subject was ADA negative at baseline, then this subject will be considered TEAR positive if any post-baseline observed or imputed value was ADA positive; otherwise, the subject will be considered TEAR negative. The imputed titer values will not be considered in subjects who are ADA negative at baseline.

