If the subject was ADA positive at baseline, then the imputed titer values will be used. The subject will be considered TEAR positive if the ADA titer at any post-baseline visit was $\geq 4\times$ the baseline titer. If none of the post-baseline titer values reached 4 times the baseline titer, then the subject will be classified as TEAR negative.

For each imputation, the proportion of responders, along with standard errors, will be estimated for each treatment group, and the estimate and standard error of the risk difference will be computed. These values will be combined across imputations using PROC MIANALYZE. Subsequently, the 90% confidence interval for the risk difference will be computed using the Wald confidence limit method.

An equivalence margin will be established as a function of the TEAR rate among the Novolog subjects. Under the null hypothesis of equivalence (i.e., $H_0: p_M = p_N$), the margin can be obtained as a function of the TEAR rate in the Novolog group using the following expression (Chow S-C et al., 2003, p. 91).

$$\delta = (z_\alpha + z_\beta) \sqrt{\frac{2p_N(1 - p_N)}{n_N}}$$

Selected values for δ are provided in Table 2 of Section 5 above. If the margin falls within the 90% confidence interval for the risk difference, then equivalence of MYL1601-D and Novolog will be declared.

These steps can be executed using code similar to the following:

```
proc freq data=simdata ;
title "90% Wald confidence interval";
by _imputation_;
ods output riskdiffcol2=rdiff1;
table group*resp / riskdiff (CL=WALD column=2) alpha=0.1;
weight count;
run;

data rdiff1; set rdiff1;
keep _imputation_ row risk ase lowercl uppercl;
if row='Difference';
run;

proc mianalyze data=rdiff1;
modeleffects risk;
stderr ase;
ods output ParameterEstimates=mirisk1;
run;

ods listing;
data parms1;
set mirisk1;
lowercl = estimate - (1.645*stderr);
uppercl = estimate + (1.645*stderr) ;
run;
proc print data=parms1;
var estimate stderr lowercl uppercl;
run;
```

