8.7.2.2 Secondary/Sensitivity analyses of the primary efficacy endpoint

Several sensitivity analyses will be conducted on the primary efficacy analysis:

- 1) The primary efficacy analysis will be repeated using observed data without imputation. This analysis will be conducted on both the ITT and the PP populations.
- 2) Subjects in the MYL-1601D group who are missing ADA values, and thus a TEAR assessment, will have their TEAR status at Week 24 imputed as positive. No imputation will be done for missing values in the NovoLog® group.
- 3) A tipping point analysis will be implemented following Liublinska and Rubin (2014). See below.

The ADA TEAR rate for each treatment group, and the difference between treatments, for

subjects who are missing data during the treatment period will be summarized for all sensitivity analyses.

The number and percent of subjects with TEAR will be summarized by treatment for each study visit during the treatment period by using similar TEAR definition: ADA negative at baseline become positive at specific visit, and ADA positive at baseline and become 4-fold increase in titer at specific visit.

A by-subject listing will be provided for observed and derived variables.

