10.1 Multiple imputation

Multiple imputation will be applied to fill in missing values for ADA binary response and for ADA titer.

For binary ADA response, if baseline ADA value is missing, the missing baseline value will be imputed (6 imputations) based on binomial distribution using probability of no missing baseline values from the same treatment group. After imputations, for subjects with negative baseline ADA (Section 10.1.1) missing post-baseline binary response (positive or negative) will be imputed using logistic regression multiple imputation. For subjects who are ADA positive at baseline (Section 10.1.2), missing post-baseline ADA continuous titer values will be imputed with same treatment group non-missing subjects using continuous MI model.

The steps are summarised below:

Section 10.1.1 describes the methodology for imputation of binary response, while Section 10.1.2 covers the imputation of continuous ADA titer, and Section 10.1.3 puts them together.

10.1.1 Multiple imputation for binary ADA response if baseline ADA is negative.

For purposes of these specifications, let $RESP_x$ represent the binary value (0 or 1) at Visit x , where x takes the values 0 (for Baseline) or 8–15. The seed that will be used in the multiple imputation of ADA binary response will be 40872021.

Missing values will be obtained from logistic regression imputation on the observed values of binary response. A fully conditional specification (FCS) method will be used to impute values from a non-monotone missing data pattern.

There are 3 steps to this process:

1. Create a dataset with one record per subject, containing all values of $RESP$ for all weeks (Baseline and Weeks 2–24 on one record); that is, each record would contain variables for $RESP_0$ and $RESP_8$ – $RESP_{15}$. The subject-level $RETRIEVED$ variable described in Section 8.7.2.1 can also be generated at this time for subjects who discontinued treatment, based on whether values after treatment discontinuation

- were retrieved (set retrieved=1) or remain missing (set retrieved=0).
2. Fill in missing values to make a monotone missing data pattern, by drawing random TEAR values from the binomial distribution based on the TEAR frequencies for the given visit within treatment group.

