    resp0n resp8n resp9n resp10n resp11n resp12n resp13n
resp14n) ;
mnar model (resp8-resp15 / modelobs=ccmv(k=1));
run;
```

10.1.2 Multiple imputation for continuous ADA titer if baseline ADA positive.

For purposes of these specifications, let ADA_x represent the continuous value for ADA titer at Visit *x*, where *x* takes the values 0 (for Baseline) or 8–15. The seed that will be used in the multiple imputation of ADA titer will be 41671703.

There are 3 steps to this process:

1. Create a dataset with one record per subject, containing all values of ADA for all weeks (Baseline and Weeks 2–24 on one record); that is, each record would contain variables for ADA₀ and ADA₈–ADA₁₅. The subject-level RETRIEVED variable described in Section 8.7.2.1 can also be generated at this time for subjects who discontinued treatment, based on whether values after treatment discontinuation were retrieved (set retrieved=1) or remain missing (set retrieved=0).
2. Run 30 Markov Chain Monte Carlo (MCMC) imputations to make the missing

values in the dataset have a monotone missingness pattern. This will produce a dataset with an index variable `_imputation_` and otherwise the same variables as the input dataset. It will have one record per imputation per subject.

3. Run a pattern mixture model regression imputation on each imputed dataset from Step 2. This will generate a dataset with the same structure as the input dataset, but will have the missing values filled in.

Step 1.

The dataset for this imputation has to put the values for all weeks onto one record. That is, the dataset would have one record per subject, with 8 values for ADA0 and ADA8-ADA15. One way this can be accomplished is the following:

```
data analysis (keep=usubjid trtp ADA0 ADA8-ADA15);
set indata;
by usubjid avisitn;
array y {9} ADA0 ADA8-ADA15;
retain ADA0 ADA8-ADA15;
if first.usubjid then do;
    ada0 = base;
    do visit = 8 to 15;
        y{visit} = .;
    end;
end;
do visit = 8 to 15;
    if avisit = visit then y{visit} = aval;
end;
if last.usubjid then output;
run;
```

Step 2.

```
/** step 2: Create monotone missingness using MCMC
imputation */
proc mi data=analysis seed=41671703 nimpute=1
out=outdata1;
mcmc impute=monotone;
var ada0 ada8-ada15;
run;
```

Step 3.

```
/***/ step 3: Perform PMM regression imputation ***/  
proc sort data=outdata1;  
run;  
  
/***/ Code to use if >=6 retrieved subjects per arm ***/  
proc mi data=outdata1 seed=41671703 nimpute=30  
out=outdata2;  

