class retrieved;  
monotone reg(ada8-ada15 / details);  
mnar model (ada8-ada15 / modelobs=(retrieved=1));  
var ada0 ada8-ada15;  
run;  
  
/***/ Code to use if <6 retrieved subjects per arm ***/  
proc mi data=outdata1 seed=41671703 nimpute=30  
out=outdata2;  
by treatment;  
monotone reg(ada8-ada15 / details);  
mnar model (ada8-ada15 / modelobs=ccmv(k=1));  
var ada0 ada8-ada15;  
run;
```

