10.1.3 Combining the multiple imputation results to derive TEAR status

At this point there should be two sets of imputed data, each containing 30 records per subject, with all visits on the same record. These will need to be merged by subject and imputation. Then the TEAR values will be computed for each subject and analyzed. There are 3 steps:

1. Merge the imputed ADA binary response dataset with the imputed ADA titer dataset, by `usubjid avisitn _imputation_`. Then generate TEAR responder status based on the Week 24 (Visit 15) ADA values using the same algorithm as was used for the original data. This dataset will have one record per imputation per subject, but the TEAR values will be non-missing for all subject visits. Note that the variable TEAR may vary from imputation to imputation for the same subject. That is supposed to happen.
2. Run the primary efficacy analysis to create the 90% confidence interval using the Wald confidence limit method within each imputation. That will result in 30 confidence intervals, one for each imputation.
3. Combine the 30 confidence intervals to generate one summary confidence interval to be presented in the table.

Step 1.

Merge the imputed titer values by `usubjid avisitn _imputation_` to make a single dataset. Then create a new variable for TEAR status by following the ADaM specs for the definition of TEAR events, but using the new imputed ADA data. Again, the dataset will contain one record per imputation per subject, with a new response variable added to every record. For the purposes of the next steps below, this new response variable will be called TEAR.

- a. If the subject was ADA negative at baseline then do:
 - i. If any of RESP8–RESP15 is positive, then TEAR=1 for that imputation for that subject
 - ii. Else TEAR=0 for that imputation for that subject
- b. Else if subject was ADA positive at baseline then do:
 - i. If $ADA_x / ADA_0 \geq 4$ for any visit, where x is in 8–15, then TEAR = 1;
 - ii. else TEAR=0

Step 2.

Use code similar to what was used to analyze the primary efficacy endpoint, but run the code by `_imputation_`. For example,

```
/** step 2: Analyze the imputed datasets */  
proc freq data=imputed;  
by _imputation_;  
table trt*tear / alpha=0.10 riskdiff (cl= wald column=2)  
;  
output=outmi riskdiff;  
run;
```

Step 3.

Combine the 30 estimated statistics into one using PROC MIANALYZE.

```
proc mianalyze data=outmi;  
modeleffects _rdif1_ ;  
stderr e_rdif1;  

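### Missing titers in baseline-positive subjects are imputed by normal regression on the raw titer scale, although TEAR is a 4-fold ratio, so noise alone turns some low-titer subjects TEAR positive

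*SAP*

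**What the plan says.** The assay produces a titer on a geometric scale. Protocol 6.5.2.4 states: "All confirmed positive samples will be evaluated for titer (Tier 3) by serially diluting the samples (2-fold dilution steps"), with the titer taken as the interpolated dilution at a cut point.

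SAP 8.7.2.1 describes the imputation of binary response by logistic regression, "while ADA titer will use a continuous-valued regression", with all prior visits as predictors. SAP 10.1 adds that, for baseline-positive subjects, "missing post-baseline ADA continuous titer values will be imputed with same treatment group non-missing subjects using continuous MI model".

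The code in SAP 10.1.2 defines ADA0 and ADA8–ADA15 as the titer. It makes the pattern monotone with "mcmc impute=monotone" and fills the rest with "monotone reg(ada8-ada15 / details"). Neither the text nor the code names a transformation, a minimum or a lower bound.

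The imputed values then decide the endpoint. SAP 8.7.2.1 counts a baseline-positive subject as "TEAR positive if the ADA titer at any post-baseline visit was" at least four times the baseline titer. SAP 10.1.3 Step 1 codes this as ADAx/ADA0 ≥ 4, which makes sense only if ADAx is the raw titer.

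**The concern.** MCMC imputation and monotone linear regression both assume normal errors with one residual variance. On raw titer that variance is set mainly by subjects with high values. The TEAR threshold, however, scales with each subject's own baseline. For illustration, a subject at titer 8 must gain 24 units to reach 32, and a subject at 64 must gain 192 to reach 256, yet the model gives both the same residual SD. The low-titer subject can cross the line by noise, and the any-visit rule allows up to seven chances. Impossible negative titers are a symptom of the same misfit. They score as TEAR negative and do not cause the false positives.

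These artificial events enter the primary analysis. They raise the NovoLog rate, which sets the margin, and they shift the treatment difference if missingness differs between arms.

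There is also a smaller specification gap. Titers are run only on confirmed-positive samples, and the SAP does not say what enters the titer model when a baseline-positive subject's later sample is ADA negative. SAP 10.1.3 says only: "Then create a new variable for TEAR status by following the ADaM specs for the definition of TEAR events". Those specifications are not included. Read literally, an observed non-event could be imputed.

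**Working it through.** **1. The plan's own margins.** SAP 8.7.2.1 gives the margin as (z_α + z_β)·√(2p(1−p)/n). With the quantiles in the SAP 10.2 code (0.95 and 0.90) and n = 250, it is (1.645 + 1.282)·√(2p(1−p)/250). This gives 5.70, 7.85, 10.47, 11.99 and 13.09% at p = 5, 10, 20, 30 and 50%. All 12 entries of SAP Table 2 reproduce to within 0.05 points.

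**2. First simulation.** The assumptions are not from the documents: log2 titer = N(4, between-subject SD) plus N(0, 0.5) at baseline and at the seven sampled post-baseline visits, with no true change. The last 1, 3 or 7 visits are missing. Sequential regression on all prior visits, with parameter draws, is fitted on 60 or 120 complete subjects. Subjects already TEAR positive are excluded. Percent called TEAR positive:

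| Visits missing | Raw, SD 0.7 | Raw, SD 1 | Raw, SD 1.5 | Raw, SD 2 | Log2 scale | Truth |
|---|---|---|---|---|---|---|
| 1 | 0.7 | 2 | 5–6 | 9–11 | 0.2–0.5 | 0.1–0.2 |
| 3 | 2–3 | 5 | 12–14 | 22–25 | 0.9–1.6 | about 0.5 |
| 7 | 5–6 | 12 | 24–26 | 38–40 | 2.0–3.1 | about 1.4 |

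With between-subject SD 0.5–0.7 and within-subject SD 0.3, the effect is near nil (at most 0.4% against 0.0%, large-sample fit).

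**3. Independent second simulation.** This used natural-log SDs (divide by 0.693 for log2), median titer 8, 100 baseline-positive subjects per arm, and 10% dropout at a random visit. The model was fitted to complete cases with parameter draws. Percent called TEAR positive among subjects with missing titers:

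| Between / within SD, natural log (log2) | Truth | Raw | Log |
|---|---|---|---|
| 0.3 / 0.35 (0.43 / 0.50) | 0.7 | 1.2 | 1.3 |
| 0.7 / 0.35 (1.01 / 0.50) | 0.5 | 6.4 | 1.4 |
| 1.0 / 0.35 (1.44 / 0.50) | 0.7 | 14.7 | 1.4 |
| 1.0 / 0.5 (1.44 / 0.72) | 6.1 | 24.9 | 8.6 |
| 1.5 / 0.35 (2.16 / 0.50) | 1.3 | 32.5 | 1.6 |

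The excess sits in the low titers. In the third row, the lower half of baseline titers has truth 1.1%, raw 28.6% and log 2.0%. In the last four rows, 23–49% of subjects with missing data receive at least one negative titer.

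**4. Trial level.** Assume 6–12 baseline-positive subjects with undetermined status per arm of 250, imputed positive at 5–25%. The arm rate then gains 6 × 0.05/250 = 0.12 points to 12 × 0.25/250 = 1.2 points. These are gross figures; net of a 1.4% true rate the upper end is 12 × 0.236/250 = 1.13 points.

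- *Balanced missingness.* At p = 10% the margin is 7.85 and the 90% CI half-width, 1.645·√(2p(1−p)/250), is 4.41, so the tolerable observed difference is 7.85 − 4.41 = 3.44 points. At p = 11.2% it is 8.25 − 4.64 = 3.61 points.
- *Unbalanced missingness.* With 4 against 12 such subjects at 25%, the difference shifts by (3 − 1)/250 = 0.8 points.

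A second route is share baseline positive × share missing × net excess. At 40%, 10% and 14 points this is 0.56 points, or 1.4 subjects of 250. Over 20–60% positive, 5–15% missing and 0–31 points excess, it runs from 0 to about 2.8 points.

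**The case against.** **Size.** With balanced missingness the tolerable difference moves by only 0.17 points, and only at the top of the assumed range. The 0.8-point shift needs both a marked imbalance and a 25% false-positive rate, and nothing in the documents supports either. This stands: the upper figures are illustrative.

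**Assay floor.** The simulations have no lowest reportable titer, and the lowest titers drive the effect. A rerun with 80 complete subjects and an assumed floor (none / 2² / 2³) gave 5.0 / 3.4 / 1.2% at SD 1 with three visits missing, and 24.3 / 20.3 / 13.4% at SD 1.5 with seven missing. A floor shrinks the effect but removes it only at small spread.

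**Branch.** Only the complete-case branch was simulated. With at least six retrieved dropouts per arm, SAP 8.7.2.1 fits the model to retrieved subjects, so the sizes above do not cover that branch. It uses the same untransformed regression.

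**Example code.** The quoted sentence in 8.7.2.1 does not say normal or raw, and the appendix is labelled as example code. But that code defines the variable as the titer and scores the plain ratio, and nothing in either document calls for another scale.

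**Safeguards.** SAP 8.7.2.2 says "The primary efficacy analysis will be repeated using observed data without imputation". It also sets every MYL-1601D subject with missing TEAR status to positive, and the tipping-point grid in 8.7.2.3 covers every possible count in both arms. None of these uses the titer model, so together they bound the effect. They do not repair the primary estimate, which is the one that decides equivalence.

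**ADA-negative samples.** SAP 7.2.1 limits missing data to absent ADA results that leave TEAR status undetermined, so the intent is partly stated. This is a secondary point, and the conclusion does not depend on it.

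**Conclusion.** The concern holds. As written, the primary analysis uses a constant-variance normal model on raw titer for an endpoint defined as a ratio, and this creates artificial TEAR positives among low-titer baseline-positive subjects. The direction is clear and the two simulations agree. The size depends on titer spread, the share baseline positive, the amount and balance of missing data, and any assay floor, none of which the documents give. At moderate spread the false rate in affected subjects is several percent to about a quarter, against a truth of about 1%; with homogeneous titers it is negligible. The effect on the equivalence conclusion is probably modest: a slightly wider margin if missingness is balanced, and a shift of up to about 0.8 points in the unbalanced example. It should be corrected because it is an avoidable bias in the primary analysis, not because it is likely to overturn the result.

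**What to change.** - In SAP 8.7.2.1 and 10.1.2, state that log2(titer) is imputed, and use it in both the MCMC and the regression steps.
- In SAP 10.1.3, score TEAR as a log2 difference from baseline of at least 2, which is identical to the 4-fold rule, or back-transform before taking the ratio.
- State that an ADA-negative post-baseline sample in a baseline-positive subject is an observed non-event at that visit and is never imputed for TEAR. If a number is needed as a predictor, or a confirmed-positive sample has no reportable titer, fix the value in advance, for example below the lowest reportable titer.

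The cost is one transformation step, one changed derivation line and two or three sentences, with no new data. The one small drawback is that a fixed value for ADA-negative samples puts a point mass in the regression, so that value should be varied in a sensitivity run.
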